8.2 Recording of Adverse Events

At each contact with the subject, the investigator will seek information on adverse events by specific questioning and, as appropriate, by examination. Information on all adverse events will be recorded immediately in the source document, and UADEs and severe, expected AEs at least probably related to the study treatment will also be recorded on the Adverse Event CRF. All clearly related signs, symptoms, and abnormal diagnostic laboratory or procedure results will be recorded in the source document.

All observed or volunteered adverse effects (serious or non-serious) and abnormal test findings, regardless of the treatment group or suspected causal relationship to the investigational device will be recorded in the subjects' case history. For all adverse effects, sufficient information will be pursued and/or obtained as to permit an adequate assessment of the causal relationship between the adverse effect and the investigational device. The clinical course of each event will be followed until resolution, stabilization, or until it has been ultimately determined that the study treatment or participation is not the probable cause. Serious adverse events at least probably related to study treatment that are still ongoing at the end of the study period will be followed up to determine the final outcome. Any serious adverse event that occurs after the study period and is considered to be at least probably related to the study treatment or study participation will be recorded and reported immediately upon learning of such event(s).

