Treatment outcomes for both phases will be defined as response (CDRS-R raw score <28 & CGI-I ≤2 & CGI-S ≤2), or nonresponse (CDRS-R raw score ≥28 and CGI-I ≥3) assessed using a logistic regression model with independent variables of treatment number (i.e. #10 vs. #20 vs. #30) and gender (male vs. female) will be analyzed. Assessing potential gender effects will be a secondary analysis. The primary analysis will not adjust for gender. Although we anticipate that more females than males will participate in the study, we assume that the distribution of gender will be similar between treatment arms and have no a priori reason to suspect that the efficacy of treatment will be gender specific.

Serious adverse events will be reported as noted within the application. All adverse events will be summarized according to treatment groups. Given the sample size for the current study, the statistical power for detecting differences between groups is limited. However, we will compare between groups using an exact test.

All statistical tests will be performed at the 0.05 significance level.

Secondary Hypotheses (for MCR site only):

Baseline glutamate, reported as a CSF-corrected absolute concentration and as an overlapping resonance with glutamine, will be significantly higher in both AC and L-DLPFC in depressed adolescents as measured by ^1H -MRS at 3T when compared to data derived from previously scanned healthy controls.

In comparison to non-remission subjects, depressed adolescents treated with rTMS who achieve remission (defined as a CDRS-R raw score <28 and CGI-I ≤ 2 and CGI-S ≤ 2 at treatment completion) will exhibit a greater decrease in glutamine, reported as a CSF-corrected absolute concentration percent change (baseline to endpoint) in AC and L-DLPFC as measured by ^1H -MRS at 3T.

The hypotheses will be tested using t-tests. Additionally, analyses of covariance will be performed to control for potentially important covariates or confounders, such as age or gender. Non-parametric distribution will be analyzed by non-ANOVA statistics.

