7.3 Subject Population(s) for Analysis

The primary analysis will use the intention-to-treat (ITT) population, defined as all patients who started at least one treatment session. Secondary analyses of the primary outcome will examine “completer” and “partially adherent” cohorts. The Completer Cohort will be defined as subjects treated according to the protocol with fewer than 10 rescheduled, missed, or partially completed rTMS sessions ultimately taking part in 30 treatment sessions. The Partially Adherent Cohort will have at least 20 completed or partially completed sessions without reaching the full 30-treatment threshold. Those with less than 20 completed or partially completed rTMS sessions will be analyzed within the intention-to-treat population.

8 Safety and Adverse Events

All Unanticipated Adverse Device Effects (UADEs) and severe, expected adverse events (AEs) at least probably related to the study treatment not meeting the criteria of UADE, including mania, exacerbation of depression, and suicidality will be recorded on the Adverse Event CRF and reported according to severity and the relationship of the AE to rTMS. Records of these events will be maintained and reports submitted to the FDA, regulatory sponsor, and reviewing IRBs according to local IRB policy and regulatory requirements. All other expected clinical adverse events and nonsignificant (not serious) clinical adverse events will be reported to all Principal Investigators on a periodic basis and reported to the appropriate IRB at the time of continuing review and to the FDA at the time of the Annual Report. Expected clinical adverse events and anticipated adverse device effects are those listed in Section 1.5.2.

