8.1 Definitions

Unanticipated Adverse Device Effect (UADE)

A UADE is any serious adverse effect on health or safety or any life-threatening problem or death caused by, or associated with, a device if that effect, problems or death was not previously identified in nature, severity, or degree of incidence in the investigational plan or IDE application (including a supplementary plan or application), or any other unanticipated serious problem associated with a device that relates to the rights, safety, or welfare of subjects.

Adverse Effect (Event)

Any untoward medical occurrence in a subject involved in clinical study of an investigational device; regardless of the causal relationship of the problem with the device or, if applicable, other study related treatment(s).

Severity Ratings: **Mild (grade 1)** – a transient AE easily tolerated by the patient.

Moderate (grade 2) – an AE that causes the patient discomfort and interrupts the subject's usual activities, but does not interfere with function. **Severe (grade 3)** – an AE that causes considerable interference with the patient's usual activities.

Relationship to Treatment: **Definite** – AE is related. **Probable** – AE has a strong temporal relationship and another etiology is less likely. **Possible** – AE has a strong temporal relationship but an alternative etiology is likely. **Not Related** – AE is due to underlying or concurrent illness or drug effect.

General Physical Examination Findings

At screening, any clinically significant abnormality should be recorded as a preexisting condition. At the end of the study, any new clinically significant findings/abnormalities that meet the definition of an adverse event must also be recorded and documented as an adverse event.

Hospitalization, Prolonged Hospitalization or Surgery

Any adverse event related to the device that results in hospitalization or prolonged hospitalization should be documented and reported as an unanticipated adverse device effect unless specifically instructed otherwise in this protocol. Any condition responsible for surgery

should be documented as an adverse event if the condition meets the criteria for an adverse event.

Neither the condition, hospitalization, prolonged hospitalization, nor surgery are reported as an adverse event or UADE in the following circumstances:

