8.3 Reporting of Unanticipated Adverse Device Effects and Unanticipated Problems

When an adverse event has been identified, the study team will take appropriate action necessary to protect the study subject and if required complete the Adverse Event CRF. All events suspected by the site PI to meet criteria for a UADE or severe, expected adverse event at least probably related to the study treatment, including those that might occur at MUSC, will be reported to the regulatory sponsor within 24 hours from time of event. The regulatory sponsor will evaluate the event and determine the necessary follow-up and reporting required. All events suspected by the site PI to meet criteria for moderate or mild, expected adverse

events at least probably related to the study treatment will be reported to the regulatory sponsor within 3 working days from time of event.

The regulatory sponsor will promptly review documented adverse events from both sites and determine whether they meet criteria for a UADE. If necessary the regulatory sponsor will report the results of such to the FDA within 10 working days. Thereafter the regulatory sponsor will submit additional reports concerning the effect as requested.

The site Principal Investigator(s) or designated study staff will be responsible for reporting to their IRB, within institutional guidelines, only those UADEs originating at their site. UADEs originating at other site(s) will be reported at the time of continuing review.

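### Section 7.2 promises a by-arm comparison of all adverse events, but Sections 8 and 8.2 require the Adverse Event CRF for only a severe, related subset and no specific rule brings in the rest

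*Combined protocol and SAP*

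**What the plan says.** **Analysis.** Section 7.2 (Statistical Methods) states: "All adverse events will be summarized according to treatment groups". After conceding that power is limited, it adds: "However, we will compare between groups using an exact test". Neither sentence restricts events by severity, relationship or expectedness.

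**Recording.** Section 8.2 has information on all adverse events written in the source document, and all adverse effects in the case history. It then limits the dedicated form: "UADEs and severe, expected AEs at least probably related to the study treatment will also be recorded on the Adverse Event CRF". The opening of Section 8 gives the same rule, naming UADEs and severe, expected events "at least probably related to the study treatment not meeting the criteria of UADE, including mania, exacerbation of depression, and suicidality". Section 8.3 treats the form as conditional: staff "if required complete the Adverse Event CRF". Sections 1.4.2 and 9.3 also mention it only where applicable.

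**Other routes.** Under Section 8, remaining expected and non-serious events are "reported to all Principal Investigators on a periodic basis and reported to the appropriate IRB at the time of continuing review", and go to the FDA in the annual report. Sections 8.3 and 8.3.1 have certain mild or moderate expected events notified to the regulatory sponsor within three working days. Section 9.3 says sites transcribe subject source data into Medidata Rave eCRFs and complete an adverse event worksheet as needed.

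**The concern.** The event set to be analysed is wider than the event set the plan requires on the form designed to hold it. If the safety table is built from that form, it will contain only events that the investigator judged severe and at least probably related, plus UADEs.

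Safety is part of the Phase I primary objective (Section 2.1.1). The strength of a blinded, sham-controlled comparison is that an all-cause difference between arms needs no judgement about causation. Filtering on attribution gives up that strength. Section 5.2 itself allows that staff might deduce the nature of the blinded coils; if they did, attribution could differ between arms, and so could what reaches the form.

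**Working it through.** The documents state no figure on this point, so the check sets the provisions side by side.

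1. **Set to be analysed (7.2).** All adverse events, by group, exact test, 0.05 level.

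2. **Set required on the form (8 and 8.2).** UADEs, plus events that are expected, severe, and rated probable or definite. Section 8.2 says these are *also* put on the form, so the form holds a subset of what is in source.

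3. **What is left over.** Section 8.1 grades severity as mild, moderate or severe, and relationship as definite, probable, possible or not related. Leaving UADEs aside, the form's rule does not reach:
   - mild or moderate events, whatever their relationship;
   - severe events rated possible or not related. A possible rating means "AE has a strong temporal relationship but an alternative etiology is likely", so a severe event closely following treatment can still fall outside;
   - unexpected events that do not meet the UADE definition.

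   Section 1.4.2 describes sensations at the treatment site as usually mild, and Section 1.4.1 lists mild headaches from the earlier adolescent studies. The tolerability events that the protocol itself expects would therefore lie mostly outside the rule.

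4. **Whether another route carries the rest to the analysis.**

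| Route | Section | Stated to feed the analysis? |
|---|---|---|
| Source document and case history | 8.2 | No |
| Three-working-day notice to sponsor | 8.3, 8.3.1 | No; a reporting duty |
| Periodic, IRB and FDA reports | 8 | No; a reporting duty |
| Adverse event worksheet | 9.3 | Not stated; which events need it is not defined |
| Transcription of source data to eCRF | 9.3 | Possibly; general, not specific to adverse events |

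   By contrast, Section 9.3 says outright that treatment data held by the device software at MUSC go to the sponsor for the data analysis. No matching sentence covers adverse events.

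5. **Compliance check.** A site that completes the form only for the filtered events meets 8.2. A site that transcribes every event from source meets the general rule in 9.3. Both can claim compliance, and their adverse event data would differ in content.

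6. **What a test on a small subset can show (illustration).** Inputs: 38 active and 37 sham (Study Summary), assuming all are treated; two-sided Fisher test at 0.05. With *x* active subjects affected and none on sham, for the values below, p = [C(38,x) + C(37,x)] / C(75,x).
   - x = 5: (501,942 + 435,897) / 17,259,390 = 0.054
   - x = 6: (2,760,681 + 2,324,784) / 201,359,550 = 0.025

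   At least 6 against 0 is needed. This shows only that a test on a sparse, filtered subset is weak. It does not predict how many events would be filtered out.

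**The case against.** The best reply is Section 9.3. All adverse events are source data, and sites are told to transcribe source data into the eCRF, so every event could be covered. Adverse event monitoring is scheduled in Tables 4 to 6, daily during acute treatment and at every maintenance visit. Section 9.3 also distinguishes visit CRFs from adverse event CRFs, so visit forms may hold event fields. The draft CRFs (Appendices F and G) and a short stretch of text between the opening of Section 8 and Section 8.1 were not available, so this cannot be excluded. Finally, 7.2 admits limited power, the primary safety endpoint is freedom from treatment-related UADEs (3.4), the secondary one is cognition (3.5), and mania and suicidality are rated on scheduled scales.

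Much of this stands, and it limits the point to an unclear data path. It does not remove the conflict. Section 8.2 is the specific rule for adverse events and separates source from form; the rule in 9.3 is general; and the worksheet has no defined event set. Monitoring under Appendix M would check recording against the same unclear rule.

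A reader might infer that most adverse event data will be lost. The documents do not support that: every event is to be written in source. A reader might also count the severity and relationship classes outside the rule and treat the count as a share of events. Classes are not frequencies, and the documents give no event rates.

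**Conclusion.** The mismatch is real and should be fixed. As written, a dataset that follows the Adverse Event CRF rule is filtered by investigator severity and attribution and cannot deliver the all-event comparison in 7.2. Uniform entry at the two sites is not assured.

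The size cannot be put as a number of events. The consequence is bounded: ascertainment is sound in both arms, the missing entries can be recovered from source, and UADE reporting and DSMB review do not depend on this rule. It would go too far to read the point as a failure of safety oversight.

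Confidence is medium. The conclusion rests on the text supplied and on the assumption that no visit CRF or unavailable text already requires entry of every event. If one does, the defect reduces to a missing cross-reference.

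**What to change.** Change Sections 8 and 8.2 so that every adverse event in both arms is entered in the eCRF with onset and stop dates, severity, seriousness, expectedness and relationship. Keep the present severity and relationship filters for expedited reporting only. In 7.2, name that dataset as the source of an all-cause table by Phase I arm, with related events as a subset. If the visit CRFs or the worksheet already capture every event, cite them in 8.2 and 7.2 instead.

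Three minor reconciliations can be made in the same amendment; none carries the main point:
- Section 8 says "Expected clinical adverse events and anticipated adverse device effects are those listed in Section 1.5.2", but the supplied text has no such section; anticipated risks are in 1.4.2, which 8.5 cites.
- The three-day notice for mild or moderate events is limited to at least probably related events in 8.3, while the MUSC text in 8.3.1 states no such limit.
- Section 8 names mania, exacerbation of depression and suicidality in its rule; 8.2 does not.

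**Cost.** Extra data entry at both sites, and back-entry from source for subjects already treated. No new assessment is needed, since 8.2 already has events sought at each contact and written in source. If existing forms suffice, the cost is one sentence in 8.2 and one in 7.2.

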8.3 Reporting of Unanticipated Adverse Device Effects and Unanticipated Problems

When an adverse event has been identified, the study team will take appropriate action necessary to protect the study subject and if required complete the Adverse Event CRF. All events suspected by the site PI to meet criteria for a UADE or severe, expected adverse event at least probably related to the study treatment, including those that might occur at MUSC, will be reported to the regulatory sponsor within 24 hours from time of event. The regulatory sponsor will evaluate the event and determine the necessary follow-up and reporting required. All events suspected by the site PI to meet criteria for moderate or mild, expected adverse

events at least probably related to the study treatment will be reported to the regulatory sponsor within 3 working days from time of event.

The regulatory sponsor will promptly review documented adverse events from both sites and determine whether they meet criteria for a UADE. If necessary the regulatory sponsor will report the results of such to the FDA within 10 working days. Thereafter the regulatory sponsor will submit additional reports concerning the effect as requested.

The site Principal Investigator(s) or designated study staff will be responsible for reporting to their IRB, within institutional guidelines, only those UADEs originating at their site. UADEs originating at other site(s) will be reported at the time of continuing review.

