For any adverse event occurring at MUSC, study staff will firstly follow procedures to protect the study subject. The site PI will then assess the severity and relatedness of the study treatment to the event and notify the regulatory sponsor as follows. For events suspected to meet criteria for a UADE (see section 8.1) or a severe, expected AE at least probably related to the study treatment, the regulatory sponsor will be notified within 24 hours of learning of the event. For suspected moderate or mild, expected AEs, the

regulatory sponsor will be notified as soon as possible but in no event more than three working days of the event. The regulatory sponsor will then be responsible for assessing the event and determining the subsequent follow-up and reporting requirements.

If a protocol modification is deemed necessary by the MUSC IRB, the site PI or designated study staff will notify the regulatory sponsor within five working days. The regulatory sponsor will be responsible for submitting these modifications to the FDA, Neuronetics, the DSMB, and Mayo Clinic IRB. No participants will be enrolled at either site until such modifications have been approved by the respective IRBs.

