8.6.1 Internal Data and Safety Monitoring Board

A Data and Safety Monitoring Board will be assembled to oversee the safety of the study, patients, and the scientific validity and integrity of data collected as part of the study. This DSMB will include members representing both sites and will consist of at least one non-study, Board-certified psychiatrist and at least one non-study, pediatric neuropsychologist. The DSMB will meet bi-annually to review any adverse events related to the study, ensure that appropriate actions were taken by study staff, the event resolved, and the proper agencies notified. If deemed necessary, the DSMB will make recommendations for changes to the study protocol to ensure the continued safety of study subjects and integrity of study data collected. All serious adverse events will be reviewed monthly or sooner upon request. In the event of an SAE, this DSMB has also been charged with making the final decision regarding breaking the study blind. Whenever possible, the DSMB will work directly with Neuronetics and the subject's clinical physician without involving the study physicians in order to prevent study bias.

9 Data Handling and Record Keeping

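### A severe, expected adverse event rated 'possible' or 'not related' has no expedited clock to the sponsor, and the available text has no written step that takes it to the DSMB's monthly review

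*Combined protocol and SAP*

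**What the plan says.** Section 8.3 sets two clocks for telling the regulatory sponsor.

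- **24 hours:** "All events suspected by the site PI to meet criteria for a UADE or severe, expected adverse event at least probably related" (the relation being to study treatment), with the clock stated as "including those that might occur at MUSC, will be reported to the regulatory sponsor within 24 hours from time of event".
- **Three working days:** moderate or mild expected "events at least probably related to the study treatment will be reported to the regulatory sponsor within 3 working days from time of event".

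Section 8.3.1 restates the rules for MUSC. A UADE or "severe, expected AE at least probably related to the study treatment, the regulatory sponsor will be notified within 24 hours of learning of the event". The next sentence begins "For suspected moderate or mild, expected AEs" and allows three working days, with no relatedness condition.

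The opening of section 8 places mania, exacerbation of depression and suicidality in the severe, expected, non-UADE class. It then gives the residual route: "All other expected clinical adverse events and nonsignificant (not serious) clinical adverse events will be reported to all Principal Investigators on a periodic basis", with the IRB told at continuing review and the FDA in the Annual Report. Section 8.2 has every adverse event entered in the source document. It reserves the Adverse Event CRF for UADEs and for severe, expected events rated at least probable.

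Section 8.1 defines 'possible' as "AE has a strong temporal relationship but an alternative etiology is likely", and 'not related' as due to underlying or concurrent illness or a drug effect.

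On oversight, section 8.6.1 says "All serious adverse events will be reviewed monthly or sooner upon request". Section 8.5 also sets monthly review of serious events. Neither section has a relatedness filter.

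**The concern.** Every subject has current major depression, so for a suicidal act or a marked worsening the depression itself is a ready alternative explanation. A blinded site rater can reasonably choose 'possible' or 'not related'. That single-subject judgement then decides whether an expected severe event leaves the site quickly.

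The DSMB is the body placed to see an imbalance between arms: the full randomization schedule goes to its chair (5.2), and it holds the decision on unblinding (8.4, 8.6.1). A cluster of such events in one arm can be recognised only in aggregate, so the DSMB must receive the events first. The CRF restriction also works against section 7.2, which plans to summarise all adverse events by treatment group and compare the groups with an exact test.

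**Working it through.** The plan gives no figure to reproduce, so the check sets the rules side by side.

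**Step 1: sponsor clock.** Inputs are the three severity grades (mild, moderate, severe) and four relatedness ratings (definite, probable, possible, not related) in 8.1. For expected events that are not UADEs this gives 3 × 4 = 12 cells.

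| Expected, non-UADE event | Cells | Clock in 8.3 | Clock in 8.3.1 (MUSC) |
|---|---|---|---|
| Severe; definite or probable | 2 | 24 hours | 24 hours |
| Severe; possible or not related | 2 | none | none |
| Mild or moderate; definite or probable | 4 | 3 working days | 3 working days |
| Mild or moderate; possible or not related | 4 | none | 3 working days |

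- 8.3: 2 + 4 = 6 cells have a clock; 12 − 6 = 6 have none.
- 8.3.1: 2 + 4 + 4 = 10 cells have a clock; 12 − 10 = 2 have none, and both are severe.

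The two sections conflict on the third and fourth rows' condition: 8.3 requires 'at least probably related' for mild and moderate events, 8.3.1 does not. They also start the clock differently for severe events, at the event in 8.3 and at learning of it in 8.3.1.

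**Step 2: severity is not seriousness.** The clocks run on severity grade. A serious event graded moderate and rated 'possible' has no clock under 8.3 and three working days under 8.3.1.

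**Step 3: other routes for a severe, expected event rated 'possible'.**

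- Opening of section 8: periodic, continuing-review and annual reporting.
- 8.1, hospitalization: a device-related event leading to admission is reported as a UADE, which brings the 24-hour clock. Whether 'related' includes 'possible' is not stated, and admission for the target disease is exempt unless the investigator judges it a worsening. An event without admission is not covered.
- 8.1, frequency: the UADE definition and both sites' IRB definitions extend to higher-than-expected incidence or frequency. Someone must already have pooled the events to apply these.
- 8.3: the sponsor reviews documented events promptly, with no number of days.
- 1.4.2: after a treatment-related mood or suicidality SAE, the family and treating physician are told. The sponsor and DSMB are not named there.

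**Step 4: route to the DSMB.** In the available text, two written steps carry an individual event to the DSMB: the copied FDA form for a UADE (8.3.2) and the seizure route (1.4.2). Section 1.4.2 treats verified mania, exacerbation of depression and worsened suicidality as SAEs when treatment-related, so they fall within the monthly review, but no written step delivers them as such.

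**Step 5: where it bites.** The regulatory sponsor is also the MCR site PI (4.3.1), and 8.3.1 has the sponsor assess any adverse event at MCR. The sponsor-clock gap is therefore mainly a MUSC matter: 25 of 75 planned subjects, one third. The DSMB step concerns all 75.

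**The case against.** The strongest reply is that the plan has several nets. All adverse events are in source documents whatever the suspected cause. The DSMB reviews serious events monthly and other adverse events every six months. The hospitalization and frequency clauses catch some cases. For mania, section 4.4.1 can be read as treating the confirmed, treatment-induced form as a UADE, although section 8 lists mania as outside that class. Appendix N, on the DSMB, is listed in section 14 but is not in the available text, and section 8.6 promises a separate data and safety-monitoring plan. Either may hold the missing step.

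Much of this stands, and it rules out three stronger readings that a reader might infer.

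- *These events have no reporting route at all.* They have a slow one. What is absent is an expedited sponsor clock.
- *The plan excludes them from DSMB review.* It does not: 8.5 and 8.6.1 apply no relatedness filter. The available text lacks a feeding step, and a missed monthly review is an inference from that.
- *Milder events are reported sooner than severe ones.* At equal relatedness this holds only under 8.3.1 as worded, whose missing qualifier may be a drafting slip. Under 8.3 a mild event rated 'possible' has no clock either.

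None of the nets reliably catches a severe suicidal or depressive event that is rated 'possible' and does not lead to admission.

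**Conclusion.** The gap is real and written into the rules. Severe, expected, non-UADE events rated below 'probable' have no expedited sponsor clock under either section: 2 of the 6 cells without a clock in 8.3, and both of the 2 in 8.3.1. This is a stated filter working against a stated safety review, so it is more than missing detail.

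The conclusion rests on two assumptions. The first is that blinded raters will sometimes attribute suicidality or worsening to the underlying depression; the documents give no rate, so the number of events affected cannot be estimated. The second is that Appendix N and the monitoring plan do not already set the step to the DSMB. If they do, the DSMB part reduces to a missing cross-reference, while the sponsor-clock and CRF parts remain.

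**What to change.** 1. In sections 8, 8.2, 8.3 and 8.3.1, remove the 'at least probably related' condition from sponsor notification and Adverse Event CRF recording for severe or serious events. Both sites then notify the sponsor within the existing 24-hour window, counted from learning of the event, whatever the relatedness rating.
2. Define 'serious adverse event' once, using subject-level harms: death, life-threatening event, hospitalization, disability and birth defect, plus mania, exacerbation of depression and suicidality as 1.4.2 already defines them. Do not import the whole seriousness list from the Mayo IRB definition in 8.1, which includes confidentiality breaches, publications and labeling changes.
3. State that the sponsor forwards all SAEs to the DSMB in time for the monthly review, or cite Appendix N if it says so.
4. Keep relatedness as a recorded field and not as a filter.
5. Reconcile 8.3 with 8.3.1 on the relatedness condition for mild and moderate events and on when the clock starts. Correct the pointer in section 8 to section 1.5.2, since the risks are described in 1.4.2.

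The cost is wording in a few sections and a modest number of extra expedited notices and CRF entries in a 75-subject, two-site trial.
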